### Amendment rationale

This protocol is being amended to correct several errors/inconsistencies, and provide clarifications. This includes:

[figure not shown]
- To correct the typographical error regarding oral/tympanic/rectal temperature versus axillary temperature.
- To correct an inconsistency regarding the requirement for blinding the technician performing microscopy readings. Since this is an open label study, blinding of technicians is not required.
- To remove serum phosphorus and uric acid assessment from the list of blood chemistry tests since these tests are normally not part of a routine laboratory assessment. There is no signal in the pre-clinical and clinical data collected so far to warrant measurement of these parameters.

- To remove albumin from the list of urinalysis assessment. As protein is already being assessed in urine samples, it is not required to have albumin in addition.
- Terms “Biochemistry” and “clinical chemistry” replaced by “blood chemistry” to maintain consistency throughout the protocol.
- The terms prior medication and concomitant medication have been defined for further clarity to make it consistent with existing information in protocol.
- To clarify that in case of treatment discontinuation, patients may be given rescue medication at the discretion of the investigator.
- For further clarification, time window for electrocardiogram (ECG) assessment has been added in the table of assessment as ECG and pharmacokinetic (PK) assessments should be aligned.
- Clarification on how some cardiac alerts should be reported. Resting heart rate < 50/min with > 25% decrease from pretreatment baseline verified by ECG should be reported to Sponsor as adverse event (AE).

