On the other hand, increased KAF156 exposure was unanticipated and there is no sufficient data to cover for exposure for the highest doses of KAF156 in this study, should KAF156 exposure increase by 2 fold. The dog data suggest that increased KAF156 exposure potentially occurs because of interaction of LUM-SDF with KAF156 at absorption-level which in turn suggest that interaction may not lead to more than 2 fold increase in KAF156 exposure in human given its estimated bioavailability of at least 50% in humans. There is no experience of KAF156 exposure beyond that of 1200 mg single dose or 600 mg daily for 3 days. Given the above situation, the first part of the study will explore the PK and safety of KAF156 given in combination with LUM-SDF to understand the impact of LUM-SDF on KAF156 exposure as victim drug. In the unlikely scenario of an increase in KAF156 exposure beyond the acceptable limit, doses in Part A of the study may be adjusted (as described in Section 3.3).

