#### **PK Run-in Part;**

Male and female adult/adolescent patients ( $\geq 12$  years old and  $\geq 35.0$  kg) will be enrolled in the PK Run-in Part. 12 patients will be dosed with a single dose of 200 mg KAF156 and 960 mg LUM-SDF. Study procedures and assessments are the same as in the 1-day cohorts in Part A with rich PK.

The drug-exposure results of the PK Run-in Part will be evaluated by the sponsor and trigger the start of Part A with KAF156 dosing as planned, or lead to a dose adaptation in Part A in case an interaction is shown between LUM-SDF and KAF156. Following this evaluation of drug-exposure, all investigators will be informed of the results and IRT/dosing will be implemented as specified in [Table 3-1](#) and [Appendix 5](#).

Patients in the PK Run-in cohort in whom the drug exposure cannot be established due to vomiting or drop-out, will be replaced by additional patients in order to achieve a total of 12 patients with evaluable exposure results in the PK Run-in Part.

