## **6 Visit schedule and assessments**

Patients must be seen for all visits on the designated day, or as close to it as possible. Missed or rescheduled visits should not lead to automatic discontinuation. Patients who prematurely discontinue the study for any reason should be scheduled for a visit as soon as possible, at which time all of the assessments listed for the final visit in the Epoch will be performed. At this final visit, all dispensed investigational product should be reconciled and the adverse event and concomitant medications recorded on the eCRF. An overview of the specific CRF pages are listed on [Table 6-5](#) (for database development purposes). The PK Run-in Part will follow the same visit schedule as for Cohorts 1 and 2 which have QD dosing for 1 day.

UNS = Unscheduled visit

EOT = End of Treatment

PSW = Premature Study Withdrawal

X = assessment to be recorded on clinical database

S = assessment to be recorded on source documentation only

 Patients will be admitted to the hospital on Day 1 and will remain in the hospital under close supervision until they are discharged by the investigator or designee on Day 4.

 Visit structure given for internal programming purpose only.

 Fever monitoring will be done every 6 hours until resolution of fever, defined as being afebrile for 24 hours.

 Comparator only (Coartem®). Coartem® will be given at 0, 8, 24, 36, 48 and 60 hours. For all drug administrations actual time should be recorded.

 Not applicable to 1-day treatment regimen.

 Not applicable to 1 and 2-day treatment regimens.

 A complete physical examination will be performed by the investigational staff at screening and include the examination of general appearance, skin, neck (including thyroid), eyes, ears, nose, throat, lungs, heart, abdomen including splenomegaly, back, lymph nodes, extremities, vascular and neurological. Malaria signs and symptoms, body height and body weight will also be recorded at screening as part of the complete physical examination.

An abbreviated physical examination will be performed at all other visits starting from Day 1. An abbreviated physical exam will include the examination of general appearance and malaria signs and symptoms. Body weight will also be measured at End of Study Visit (Day 43 or earlier in case of premature patient discontinuation).

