**Table 6-2 12-Lead ECG assessments (triplicate) for all patients (PK Run-in Part, Part A and Part B)**

Epoch	Screen		Treatment 														Follow-up						UNS		
	1	99	101						102				199				201	202	203	204	205	299			
Visit Numbers 													EOT Epoch / premature discontinuation									End of Follow up / PSW			
Study Day			1						2				3				4	5	8	15	29	43			
Window			±0 day						±0 day				±0 day				±0 day	+1 day	±1 day	±2 day	±4 days	±4 days			
Time (post-dose) in hours	-24 to <0		0	1	3	6	8	12	18	24	27	30	36	48	51	54	60	68	72	96	168	336	672	1008	
KAF-LUM SDF 1D cohort		x			x	x			x 	x		x 									x			x	
KAF-LUM SDF 2D cohort		x				x 				x	x	x		x							x			x	
KAF-LUM SDF 3D cohort		x				x 				x				x	x	x			x		x			x	
Coartem cohort		x				x 											x				x			x	

**Note: ECG's should be taken in triplicate within 5 minutes after resting for at least 10 minutes in the supine position to ensure a stable heart rate according to the ECG investigator manual. Also, ECG's should be taken before any other procedure taken at the same nominal time point is performed. For Scheduled time ≤ 2 h ± 10 min; 2 to < 24 h ± 30 min; ≥ 24 to 72 h ± 2 h; > 72 h ± 24 h.**

UNS = Unscheduled visit

EOT = End of Treatment

[figure not shown]
PSW = Premature Study Withdrawal

X = assessment to be recorded on clinical data base

 Patients will be admitted to the hospital on Day 1 and will remain in the hospital under close supervision until they are discharged by the investigator or designee on Day 4.

 Visit structure given for internal programming purpose only.

 ECG assessment at this time point to be done for patients in Part A only, ECG assessments will be repeated in case of abnormalities.

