**Table 6-3 PK sampling schedule for patients involved in RICH PK sampling (PK Run-in Part and Part A)**

Epoch	Screen		Treatment 														Follow-up					UNS															
Visit Numbers 	1	99	101							102							199														299 End of Follow up / PSW						
			EOT Epoch / premature discontinuation														201	202	203	204	205																
Study Day			1							2							3														4	5	8	15	29	43	
Window			±0 day							±0 day							±0 day														±0 day	+1 day	±1 day	±2 day	±4 days	±4 days	
Time (post-dose) in hours	-24 to <0		0	1	3	6	8	12	18	24	27	30	36	48	51	54	60	68	72	96	168	336	672	1008													
KAF-LUM SDF 1D cohort			X 	x	x	x		x	x	x		x		x					x	x																	
KAF-LUM SDF 2D cohort			X 	x	x	x		x		x	x	x	x	x				x	x	x																	
KAF-LUM SDF 3D cohort			X 	x	x	x		x		x				x	x	x		x	x	x	x																

**Notes:** A) Each PK sample will be 1mL blood. Further details on sample collection, numbering, processing and shipment can be found in the Site Operations Manual. B) Missed PK sampling time should be taken as soon as possible and actual time should be recorded. For Scheduled time ≤ 2 h ± 10 min; 2 to < 24 h ± 30 min; ≥ 24 to 72 h ± 2 h; > 72 h ± 24 h.

UNS = Unscheduled visit

EOT = End of Treatment

[figure not shown]
PSW = Premature Study Withdrawal

X = assessment to be recorded on clinical data base

 Patients will be admitted to the hospital on Day 1 and will remain in the hospital under close supervision until they are discharged by the investigator or designee on Day 4.

 Visit structure given for internal programming purpose only.

 PK sampling at Visit 101 should be done in a range of 15 min to 1 min prior to dosing.

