2.8 Safety analyses

All safety analyses will be performed using the safety set. Safety data for PK run-in cohort will be summarized separately. Part A and Part B will be pooled for selected safety analysis.

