2.8.3 Other safety data

2.8.3.1 ECG and cardiac imaging data

The following quantitative variables will be summarized for averaged triplicate ECG: heart rate, RR interval, PR interval, QRS interval, QT interval, QTcB (QT interval corrected for heart rate according to Bazett) and QTcF (QT interval corrected for heart rate according to Fredericia).

Descriptive summary statistics for the change from baseline for each post-baseline visit will be performed by ECG parameters and treatment group.

Patients with notably high QT, HR and fever ($\geq 37.5^\circ\text{C}$ for *axillary* or $\geq 38.3^\circ\text{C}$ for other routes) will be provided.

To assess the temporal correlations mean change of QTcF over time, mean change of ECG HR over time, mean change of temperature over time, and PK concentration of KAF156 and lumefantrine over time will be plotted with all panels aligned on the x-axis (Time after dosing).

QTc will be summarized categorically by computing the number and percentage of patients at each time point and at the maximum post baseline value with following:

- QT, QTcF, or QTcB
 - > 450 and ≤ 480 ms
 - > 480 and ≤ 500 ms
 - > 500 ms
 - Increase from Baseline of ≥ 30 ms to < 60 ms
 - Increase from Baseline of ≥ 60 ms
- HR for age ≥ 18 years
 - Increase from baseline $>25\%$ and to a value > 100 bpm
 - Decrease from baseline $>25\%$ and to a value < 50 bpm
- HR for age < 18 years
 - $>$ upper limit of normal (ULN) defined in Table 2-3
 - $<$ lower limit of normal (LLN) defined in Table 2-3
- PR

- Increase from baseline >25% and to a value > 200 ms
- New value of > 200 ms
- QRS
 - Increase from baseline >25% and to a value > 120 ms
 - > 120 ms

Table 2-3 Normal heart rates (resting) by age

Age (years)	Normal range bpm
1 - ≤ 3	70 - 110
3 - ≤ 6	65 -110
6 - ≤12	60 -95
>12	55 -85

Source: Nelson Textbook of Pediatrics, 18th Edition

A line plot by patient (Spaghetti plot) will be provided by visit and treatment group.

In addition, shift tables comparing baseline ECG results (normal, abnormal, not available, total) with the post-baseline results will be provided by visit and at the worst post-baseline result (normal, abnormal, not available, total).

A listing of all newly occurring or worsening abnormalities as compared with baseline will be provided, as well as a by-patient listing of all quantitative ECG parameters.

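### Read literally, footnote 3 of Table 6-2 denies PK run-in patients the 18 h and 30 h ECGs that Section 3.1 gives them, leaving 5 of 7 post-dose ECGs

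*Protocol*

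**What the plan says.** The title of protocol Table 6-2 covers the PK run-in, Part A and Part B. Its 1-day row has post-dose triplicate ECGs at 3, 6, 18, 24, 30, 168 and 1008 h. The 18 h and 30 h cells carry footnote 3: "ECG assessment at this time point to be done for patients in Part A only".

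Three other places describe what run-in patients should have:

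- Protocol Section 3.1, repeated in SAP Section 1.1: "Study procedures and assessments are the same as in the 1-day cohorts in Part A with rich PK".
- Protocol Section 6, on visits: "The PK Run-in Part will follow the same visit schedule as for Cohorts 1 and 2 which have QD dosing for 1 day".
- Protocol Table 6-3, whose title names the run-in and Part A. Its 1-day row draws rich PK at both 18 h and 30 h, with no restriction by part and with the same time windows as Table 6-2.

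On purpose and analysis, protocol Section 1.1 says "the first part of the study will explore the PK and safety of KAF156 given in combination with LUM-SDF". SAP Section 2.8 says "Safety data for PK run-in cohort will be summarized separately". SAP Section 2.8.3.1 tabulates QTc by "number and percentage of patients at each time point and at the maximum post baseline value".

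**The concern.** Section 3.1 presents the run-in as distinct from the two main parts, A and B, so a footnote limited to Part A leaves it out on its plain wording. Section 3.1 also gives the run-in everything that the 1-day Part A cohorts have, and those cohorts have both ECGs. A site cannot follow both instructions. The assessment tables are what sites use day to day, so a site could take the 18 h and 30 h blood samples from a run-in patient without the ECG.

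Run-in patients are the first to receive KAF156 and LUM-SDF together, and safety is a stated purpose of the part. Under the footnote:

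- they have no scheduled ECG between 6 h and 24 h;
- no ECG accompanies the 18 h and 30 h PK samples;
- their last scheduled ECG before discharge is at 24 h instead of 30 h.

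Because run-in safety is summarised on its own, its QTc table would be empty at two time points unless unscheduled ECGs happened to fall in those windows. The rationale for Amendment 2 gives the reason for the ECG time windows now in Table 6-2: "ECG and pharmacokinetic (PK) assessments should be aligned". Dropping the ECG at two PK times sits badly with that aim.

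**Working it through.** The plan states no figure to reproduce. The check is a count of cells in the 1-day rows of Tables 6-2 and 6-3, matched to the time header by column position.

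| Hours after dose | ECG, Part A 1-day cohorts | ECG, run-in under footnote 3 | Rich PK, run-in |
|---|---|---|---|
| 1 | – | – | yes |
| 3 | yes | yes | yes |
| 6 | yes | yes | yes |
| 12 | – | – | yes |
| 18 | yes | **no** | yes |
| 24 | yes | yes | yes |
| 30 | yes | **no** | yes |
| 168 | yes | yes | not counted |
| 1008 | yes | yes | not counted |

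The screening ECG and the pre-dose PK sample are left out. PK is counted only up to 30 h. SAP Table 5-6 defines ECG analysis windows for both 18 h and 30 h, which agrees with the column matching.

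**ECGs per patient.** Seven cells are marked and two carry the footnote: 7 − 2 = 5.

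**Over the run-in.** 2 × 12 = 24 triplicates. Twelve is the planned number of patients with evaluable PK. Each replaced patient could add two more.

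**ECG times that coincide with a PK draw, up to 30 h.** With the footnoted cells: 3, 6, 18, 24 and 30 h, so 5 per patient and 5 × 12 = 60 in all. Without them: 3, 6 and 24 h, so 3 per patient and 3 × 12 = 36. The fall is (60 − 36)/60 = 40%.

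**Longest interval between scheduled post-dose ECGs up to 24 h.** With the 18 h ECG: 6 h to 18 h, which is 12 h. Without it: 6 h to 24 h, which is 18 h.

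**Other rows.** Footnote 3 also marks the 6 h ECG in the 2-day, 3-day and Coartem rows. The run-in has a single 1-day cohort, so those cells do not concern it.

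**The case against.** The strongest reply is that the documents already settle the question. Section 3.1 is the rule written specifically for the run-in, the SAP repeats it, and Section 6 gives the run-in the visits of Cohorts 1 and 2. Table 6-4, the sparse PK schedule, restricts the same 18 h and 30 h cells of its 1-day row to Part A. Its title covers only Parts A and B, so the contrast there can only be with Part B. Footnote 3 of Table 6-2 was probably meant the same way. This stands as an account of intent. It does not cure the wording, because Table 6-2 names a third group that Table 6-4 does not, and the footnote as written leaves that group out.

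The size of the harm can also be challenged, and these points hold:

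- The Part A 2-day and 3-day rows have the same gap from 6 h to 24 h and no 3 h ECG. Some of those cohorts take 400 mg of KAF156 with 960 mg of LUM-SDF, twice the run-in KAF156 dose. Even under the footnote, the run-in has more ECGs on Day 1 than they do.
- No analysis visible in the SAP uses paired ECG and PK observations as its unit. Section 2.8.3.1 plots mean QTcF change and concentrations in panels on a shared time axis. The 40% fall is therefore descriptive only. Table 6-3 also has PK draws at 1 h and 12 h with no ECG for any part, so alignment never meant an ECG at every draw.
- Protocol Section 6.5.5 and Appendix 3 call for repeat ECGs when QTc thresholds are met, whatever the schedule.
- It cannot be known that a site would follow the footnote rather than Section 3.1, only that it could.

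**Conclusion.** The concern holds as an internal inconsistency. Footnote 3 of Table 6-2, as written, contradicts Section 3.1 of the protocol and Section 1.1 of the SAP. Under the footnote a run-in patient has 5 of the 7 post-dose ECGs, up to 24 triplicates fewer over 12 patients. The count rests on two things: the column positions in the extracted tables, and a literal reading under which the run-in is not part of Part A.

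The consequence is minor. Table 3-1 makes Part A dosing depend on AUC0-24h, and the primary efficacy endpoint is untouched. The run-in uses 200 mg, the lowest planned KAF156 dose, patients are in hospital until Day 4, and ECGs at 3, 6 and 24 h remain. The correction is still worth making, because these are scheduled safety assessments in the first patients given the combination.

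**What to change.** Reword footnote 3 of Table 6-2 so that the marked ECGs are done in the *PK Run-in Part and Part A only*. Part B stays excluded, as was probably intended, and the other rows do not change.

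The cost is one footnote and at most 24 triplicate ECGs for 12 patients. These patients are in hospital and having blood drawn at both times, and Section 3.1 already calls for the ECGs, so nothing is added to what the protocol requires. If the run-in is already complete, the report should state how many run-in patients have an ECG at 18 h and at 30 h.

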**Table 6-3 PK sampling schedule for patients involved in RICH PK sampling (PK Run-in Part and Part A)**

Epoch	Screen		Treatment 														Follow-up					UNS															
Visit Numbers 	1	99	101							102							199														299 End of Follow up / PSW						
			EOT Epoch / premature discontinuation														201	202	203	204	205																
Study Day			1							2							3														4	5	8	15	29	43	
Window			±0 day							±0 day							±0 day														±0 day	+1 day	±1 day	±2 day	±4 days	±4 days	
Time (post-dose) in hours	-24 to <0		0	1	3	6	8	12	18	24	27	30	36	48	51	54	60	68	72	96	168	336	672	1008													
KAF-LUM SDF 1D cohort			X 	x	x	x		x	x	x		x		x					x	x																	
KAF-LUM SDF 2D cohort			X 	x	x	x		x		x	x	x	x	x				x	x	x																	
KAF-LUM SDF 3D cohort			X 	x	x	x		x		x				x	x	x		x	x	x	x																

**Notes:** A) Each PK sample will be 1mL blood. Further details on sample collection, numbering, processing and shipment can be found in the Site Operations Manual. B) Missed PK sampling time should be taken as soon as possible and actual time should be recorded. For Scheduled time ≤ 2 h ± 10 min; 2 to < 24 h ± 30 min; ≥ 24 to 72 h ± 2 h; > 72 h ± 24 h.

UNS = Unscheduled visit

EOT = End of Treatment

[figure not shown]
PSW = Premature Study Withdrawal

X = assessment to be recorded on clinical data base

 Patients will be admitted to the hospital on Day 1 and will remain in the hospital under close supervision until they are discharged by the investigator or designee on Day 4.

 Visit structure given for internal programming purpose only.

 PK sampling at Visit 101 should be done in a range of 15 min to 1 min prior to dosing.

**Table 6-4 PK sampling schedule for patients NOT involved in RICH PK sampling (Part A and Part B)**

Epoch	Screen		Treatment 														Follow-up						UNS						
Visit Numbers 	1	99	101							102							199						201	202	203	204	205	299	End of Follow up / PSW
			EOT Epoch / premature discontinuation																										
Study Day			1							2							3						4	5	8	15	29	43	
Window			±0 day							±0 day							±0 day						±0 day	+1 day	±1 day	±2 day	±4 days	±4 days	
Time (post-dose) in hours	-24 to <0		0	1	3	6	8	12	18	24	27	30	36	48	51	54	60	68	72	96	168	336	672	1008					
KAF-LUM SDF 1D cohort					x	x			x 	x		x 									x								
KAF-LUM SDF 2D cohort					x 	x 				x	x	x		x							x								
KAF-LUM SDF 3D cohort					x 	x 				x				x	x	x			x		x								
Coartem cohort						x 				x				x				x			x								

**Note: Missed PK sampling time should be taken as soon as possible and actual time should be recorded. For Scheduled time ≤ 2 h ± 10 min; 2 to < 24 h ± 30 min; ≥ 24 to 72 h ± 2 h; > 72 h ± 24 h.**

UNS = Unscheduled visit

EOT = End of Treatment

[figure not shown]
PSW = Premature Study Withdrawal

X = assessment to be recorded on clinical data base

 Patients will be admitted to the hospital on Day 1 and will remain in the hospital under close supervision until they are discharged by the investigator or designee on Day 4.

 Visit structure given for internal programming purpose only.

 PK sampling at these time points to be done only for patients in Part A.

**Table 6-5 Overview of specific CRF pages**

Epoch	Screen		Treatment 														Follow-up					UNS						
Visit Numbers 	1	99	101							102							199		201	202	203	204	205	299				
			EOT Epoch / premature discontinuation														End of Follow up / PSW											
Study Day			1							2							3					4	5	8	15	29	43	
Window			±0 day							±0 day							±0 day					±0 day	+1 day	±1 day	±2 day	±4 days	±4 days	
Time (post-dose) in hours	-24 to <0		0	1	3	6	8	12	18	24	27	30	36	48	51	54	60	68	72	96	168	336	672	1008				
Screening Epoch disposition page 	x	x																										
Treatment completion 			x				x 			x 			x 	x 			x 											
Treatment Epoch disposition page 																		x										
Follow-up Epoch disposition page 																									x			

UNS = Unscheduled visit

EOT = End of Treatment

PSW = Premature Study Withdrawal

X = assessment to be recorded on clinical data base

 Patients will be admitted to the hospital on Day 1 and will remain in the hospital under close supervision until they are discharged by the investigator or designee on Day 4.

 Visit structure given for internal programming purpose only.

 To be completed at the last study drug administration.

 Comparator only (Coartem®).

[figure not shown]
 Not applicable to 1-day treatment regimen.

 Not applicable to 1 and 2-day treatment regimens.

 To be completed at End of Treatment (EOT) Epoch (end of Day 3 or at the time of treatment Epoch discontinuation).

 To be completed at end of follow-up Epoch (Day 43 or at the time of follow-up Epoch discontinuation).

 The Screen Epoch disposition page is completed at Visit 1 if a patient is a screen failure at Visit 1 and at Visit 99 otherwise.

